1.0 SPECIFIC STUDY AIMS

Aims

The primary aim is to reduce acute care utilization and cost for advanced cancer patients by training and deploying health care coaches who help patients and families discuss care goals, virtual modalities, engage in shared-decision-making, and participate in educational activities.

The secondary aims are to improve patients' experience of their care including overall health and emotional and mental health status, improve patient satisfaction with care and decision-making and advance care planning.

Hypothesis

Compared to patients who receive usual advanced cancer care, patients who partner with lay health care coaches are hypothesized to experience lower rates of acute care utilization, lower numbers of emergency room visits and hospital stays within 6-months post-enrollment. Secondarily, we will explore the effect of the intervention on satisfaction with care, overall health and emotional and mental health status, from time to enrollment to 6 months post-enrollment, advance care planning documentation, and acute care use at 12-months post-enrollment and within 30 days prior to death among those who died during the 12-month follow-up period.

2.0 BACKGROUND AND RATIONALE

Advanced cancer is an incurable condition, the second leading cause of death in the United States, and incidence rates are expected to increase and costs are expected to double over the next seven years. Many patients and families currently describe a poor quality of life with difficult decisions, little understanding of the disease context, unnecessary pain and suffering, and treatment options that are often provided far from their residence. Care delivery is often fragmented with poor care coordination and lack of resource utilization closer to patient and family needs.

Often quality of life, especially at the end of life, is improved when care is coordinated, components of proactive health and well-being are adopted and elements of patient-centered care help establish the Goals of Care Plan with appropriate documentation, and when special attention is provided to allowing care delivery to be received closer to patient's neighborhood. We recognize that in any situation, goals of care may change with the delivery of care for patients with advanced cancer; however, establishing improved care coordination, care goals that provide guidance and reassurance and develop with the patient and his/her support network, and providing care in a patient-centered approach can result in significant improvements in patient experience and may ultimately help to contain health care spending.

The key elements address three major challenges: 1) patients with cancer and their families face confusing choices and difficult decisions and 2) Patients at the end of life may suffer pain or uncontrolled symptoms along with poor care coordination associated with their cancer diagnoses.

The proposed patient-centered care program addresses these three critical care elements by training and deploying health care coaches who help patients and families discuss goals for life virtual modalities, engage in shared-decision-making, and participate in educational activities.

Cancer related symptom management is addressed through the establishment of a nurse-supervised protocol-driven proactive symptom relief for patients with cancer. The desired outcomes include: 1) Identify and engage patients with advanced or newly diagnosed cancer, and to include their family members and support network in decisions about their health care plans; 2) Ensure patients and families understand prognosis and document goals for life, and link patients to health care coaches to make optimal life decisions 3) Implement established protocols and operations to improve timely symptom control and oncology care coordination.

3.0 STUDY ENROLLMENT AND PARTICIPANT ELIGIBILITY

3.1 Study Enrollment

Location

Patients will be recruited from the oncology clinics at St. Jude Hospital in Fullerton, CA.

Enrollment Procedures

Each week, the site PI and study staff will receive a list of potential patients. After the site PI and study staff conduct proper screening (see below section titled "Screening Procedures" for specific details), the staff will create a list of eligible patients and their primary oncology appointment times. At the patient's oncology appointment, the oncologist will present the study and initiate the consent procedure (see below section titled "Consent Procedures" for specific consent details).

Screening Procedures

The Site PI and staff will utilize the following documents and procedures to screen for patients who fit the inclusion criteria listed in 3.2

- Diagnosis (ICD-9) codes
- Provider Referrals (request for oncology consultation)
- Pathology results (must be positive for malignancy)
- Biopsy requests
- Abnormal test results (mammograms, colonoscopies, imaging results)

Screen failures will not be included in the study data. The PI will keep a record of history and reasons for screen failures; however, any patient information gathered during this process will be destroyed.

Consent Procedures

The oncologist will refer eligible patients to the program. The program manager or the primary oncologist will introduce will obtain consent from eligible patients at the patient's primary oncology appointment following advanced cancer diagnosis. The program manager or the oncologist will introduce the research project and provide a consent form document describing the project with sufficient information to potential participants. Patients will be provided adequate time to make an informed decision regarding their participation. Participants must sign an IRB approved informed consent document prior to participation in any study specific procedure. The participant will receive a copy of the signed and dated consent form document. The original signed informed consent document will be retained in the research file. Patients who refuse participation or have no capacity for decision-making will not be included in the study.

If a patient consents, patients will be provided a welcome letter with basic information and contact phone numbers for the project.

For all patients assigned to the health care coach, the program manager will provide the coach with the patient's phone number and the coach will contact the patient by phone to begin the intervention procedures that include: assisting patients with their goals of care, documenting goals of care, and assisting with symptom assessment. The intervention will be provided in addition to the usual care processes.

3.2 Participant Criteria

Inclusion criteria

- 1. Newly diagnosed patients for the following conditions.
 - Colon cancer stage III and IV
 - Rectal cancer stage II, III, IV
 - Glioblastoma multiforme (brain) -- no stage
 - Non-small cell lung cancer stage IIIA, IIIB, IV
 - Small cell lung cancer, limited stage and extensive stage
 - Castration-resistant prostate cancer
 - Head and neck cancer stage III and IV
 - Gastric cancer stage III and IV
 - Esophageal cancer stage III and IV
 - Pancreatic cancer stage II,III, IV
 - Renal cell carcinoma, stage IV
 - Breast cancer, stage IV, if triple negative ER/PR/H2N negative or on systemic chemotherapy
 - Sarcoma, stage IV
 - Bladder carcinoma, stage IV
 - Acute myeloid leukemia
 - Melanoma, stage III and IV
 - Ovarian cancer, stage III and IV
 - High Grade MDS

Eligibility also includes patients with recurrent cancer of any diagnosis.

- 2. The patients must be 18 years or older.
- 3. Patients must have the ability to understand and willingness to sign a written informed consent document.
- 4. Patient must have ongoing oncologic needs and plan to receive all care at the study institution and not already be in hospice or home-care.

Exclusion Criteria

The disease must be *newly* diagnosed or patients with recurrent disease of any cancer diagnosis. Patients must not already receive hospice services and palliative care.

Criteria for Removal from Study

Any patients or families of patients in the intervention arm who withdraw consent will be removed from the study. Upon removal, usual care will be restored for these patients.

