4.0 MATERIALS AND METHODS

After a patient consents, the patient will be registered and entered into the project database and assigned an identification number. The subject's identification number will be used on all subject-specific documents and research-related forms.

During registration, patients will be randomized to two arms (Arm A: Usual Care Arm B: Health Care Coach Intervention). Specifically, the patients will be randomized into two arms by cancer type.

All patients will be surveyed over the course of the study regarding patient experience with care, patient satisfaction and overall health status and emotional and mental health status (using the CG-CAHPS: Clinician and Group Consumer Assessment of Healthcare Providers and Systems), advanced care planning, and symptom assessments (using the ESAS: Edmonton Symptom Assessment Scale) and healthcare use. A member of the project team, excluding the Health Care Coach, will administer the assessments and conduct an electronic health record review of all health care use at baseline, 3, 6, 9 and 12 months post-enrollment. Participants will provide consent for health record review at external facilities by signing a health release authorization form at each of the outcome assessment time periods. The symptom assessments will be administered at baseline for each patient in the intervention and control. Participant information should be entered into the local databases within 7 calendar days.

Arm A: Usual Care (Control) / No Intervention
 Patients in this arm receive "usual" care from their care team.

Arm B: Health Care Coach Arm / Intervention Group

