5.2 Analysis Plan (see Detailed Statistical Analysis Plan Attached)

All patients will be included in the analysis based on their randomization assignment at time of enrollment. The unit analysis will be completed at the participant-level. We will conduct descriptive statistics to evaluate balance between demographic (i.e., sex, age, race/ethnicity) and clinical variables (i.e., stage of cancer, diagnosis of cancer) between both the randomized and control groups. To assess our primary outcome of the effect of the intervention on acute care use within 6-months post-enrollment we will assess % of patients with acute care use. We will create a (composite measure for acute care use that includes both ED visits and hospitalizations. To compare risk of acute care use (composite measure) and individual ED and hospital use within 6 months post-enrollment, we will use Cox regression models. We will also compare counts of total ED visits and hospitalization (composite measure of acute care use) within the first 6 months, using General Estimating Equation with Poisson family, log link, and independent correlation.

For secondary outcomes of ED and hospital use within 12 months, we will compare use using GEE models. We will compare counts of total ED visits and hospitalization (composite measure of acute care use) within 12 months, using General Estimating Equation (Poisson) with an offset term for length of follow-up. To compare goals of care discussion and documentation, Advance Directive

documentation, Physician Order for Life Sustaining Treatment documentation, Chemotherapy, Radiation, Surgery, hospice, and palliative care within 12 months, we will use GEE models to compare odds of documentation or use across groups. For end-of-life health care use, we, we will compare any ED use and hospital use prior to death (30 days prior) and proportion of participants with palliative care and hospice use using the models described above among participants who died during the 12-month study.

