For secondary outcomes, we will assess change in patient-reported outcome scores from baseline (at time of enrollment) to 6-months (post-enrollment). For satisfaction variables with responses "never", "sometimes," "usually," or "always" we will report results as the proportion of participants who respond "always" at 6-months post-enrollment compared to all other responses. For satisfaction variables with responses, "strongly disagree," "disagree," "neither agree nor disagree," "agree," or "strongly agree, we will report results as the proportion of participants who respond, "strongly agree." For overall health and overall mental and emotional health variables, responses are scores that range from 0 to 5, with lower scores indicating "very good" or "excellent" health and higher scores indicate poorer overall health. We will report results as the proportion of participants who respond, "very good" or "excellent." Missing data will not be imputed in any case. We will utilize GEE to compare changes between groups overtime from baseline (time of enrollment) to 6-months post-enrollment using GEE models with a term for an interaction between the treatment group and time (month) and clustered within person.

We will compare survival using Kaplan Meier methods and the risk of death for both groups after randomization using Cox proportional hazards regression models. All analyses will be adjusted for covariates that are found to be imbalanced between study groups, such as age, race/ethnicity, cancer stage and cancer diagnosis.

Relevant subsets of the above metrics may be measured on patients by cancer diagnosis and stage.

Sample Size Considerations

The sample size of 128 participants (64 randomized to the intervention group and 64 randomized to the control group) provides greater than 90% power to detect a 55% or greater difference in acute care use risk at 6-months follow-up. The anticipated effect size was based on our prior studies [11, 13, 18] and feedback by the oncology clinicians at St. Jude's Crosson Cancer Institute. Power calculations will not be generated for our secondary outcomes as these are considered exploratory. Statistical significance of secondary outcomes is for trends only and not represented in this sample size calculation.

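### The only removal rule names the intervention arm alone, does not separate stopping the coach from leaving follow-up, and is not reconciled with analysis by randomized assignment

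*Combined protocol and SAP*

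**What the plan says.** Section 3.2, under the criteria for removal, gives one rule: "Any patients or families of patients in the intervention arm who withdraw consent will be removed from the study". It continues: "Upon removal, usual care will be restored for these patients". No corresponding rule is given for Arm A.

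Section 5.2 defines the analysis set: "All patients will be included in the analysis based on their randomization assignment at time of enrollment". It does not say whether a removed patient's earlier data are kept, whether record review goes on, or when follow-up ends. On missing data it says: "Missing data will not be imputed in any case".

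The six-month analyses in Section 5.2 are a risk comparison ("ED and hospital use within 6 months post-enrollment, we will use Cox regression models") and a count of emergency visits plus hospitalizations ("within the first 6 months, using General Estimating Equation with Poisson family, log link, and independent correlation"). The 12-month count is specified differently, "using General Estimating Equation (Poisson) with an offset term for length of follow-up".

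Section 4.0 obtains permission to review outside records "by signing a health release authorization form at each of the outcome assessment time periods", so capture of outside care depends on the patient still taking part at each assessment.

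**The concern.** Section 3.1 makes coaching an addition to usual care. Restoring usual care after removal can therefore only mean that the coach stops. Read this way, the rule treats stopping the coach and leaving the study as one event, and only in Arm B.

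Arm B also has more occasions to withdraw. Under Section 4.0 its patients are contacted weekly to monthly for six months, while outcome assessments for both arms are at baseline and 3, 6, 9 and 12 months. Section 3.1 describes consent by patients only, and Section 4.0 makes family meetings optional, yet the rule gives families a part in removal.

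If site staff stop collecting outcomes once a patient is removed, outcome data are lost from one arm of the primary comparison. A patient who no longer signs releases will probably have outside visits and admissions missed, and nothing is imputed. A difference in acute care use could then come from the removal rule and not from the coach.

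**Working it through.** **Inputs from the documents.** 64 patients per arm and a two-sided 5% level (sample size text in Sections 5.2 and 5.3). 1.45 acute care visits per member per year (Section 5.3), so 1.45/2 = 0.725 per six months.

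**Assumptions.** The plan gives no six-month risk, withdrawal rate or risk for those who withdraw. I assume Poisson visits, so the six-month risk is p = 1 − exp(−0.725) = 0.516. I assume no true effect, and a share w of 10% or 20% of Arm B removed (about 6 or 13 of 64).

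**The plan's own figure.** Section 5.3 claims at least 90% power for a 55% difference in risk. With 0.516 against 0.45 × 0.516 = 0.232 and 64 per arm, a two-proportion calculation gives 92.2%, so the assumed risk is compatible with the claim. Losing patients from Arm B alone lowers this to 90.7% at 10% and 88.8% at 20%. Power is therefore not the main issue; bias is.

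**Case 1: removed patients are excluded from the analysis.** If their risk is q, the risk left in Arm B is r = (p − w·q)/(1 − w), and the risk ratio is r/p. For w = 0.20 and q = 0.85: (0.516 − 0.170)/0.80 = 0.432, and 0.432/0.516 = 0.84. The chance of a false significant benefit is Φ[(p − r − 1.96·se0)/se1], with se0 the pooled and se1 the unpooled standard error for 64 and 64(1 − w) patients. Its nominal value is 2.5%.

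| Risk of those removed | 10% removed: Arm B risk, risk ratio, false benefit | 20% removed: Arm B risk, risk ratio, false benefit |
|---|---|---|
| 0.516 (average) | 51.6%, 1.00, 2.5% | 51.6%, 1.00, 2.5% |
| 0.85 | 47.9%, 0.93, 6.0% | 43.2%, 0.84, 14.2% |
| 1.00 (extreme) | 46.2%, 0.90, 8.5% | 39.5%, 0.77, 25.1% |
| 0.30 | 54.0%, 1.05, 1.3% | 57.0%, 1.10, 0.5% |

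The direction depends on who leaves.

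**Case 2: removed patients are kept, but their counts stop at removal.** With no offset, and removal unrelated to risk after a fraction f of the six months, the expected rate ratio is 1 − w(1 − f). The standard error of its log is √[1/(64 × 0.725) + 1/(64 × 0.725 × ratio)].

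| Removal at | 10% removed: rate ratio, false benefit | 20% removed: rate ratio, false benefit |
|---|---|---|
| Month 2 (f = 1/3) | 0.93, 5.1% | 0.87, 9.8% |
| Month 3 (f = 1/2) | 0.95, 4.3% | 0.90, 7.1% |

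A simulation of 40,000 trials with robust standard errors, removing 6 or 13 of 64 at month 2, gave 5.0% and 9.5%.

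The percentage of patients with any use behaves the same way if removed patients stay in the denominator with no later use. At month 2, Arm B shows (1 − w) × 0.516 + w × [1 − exp(−0.725/3)], which is 48.6% (ratio 0.94) at 10% and 45.5% (ratio 0.88) at 20%.

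**Case 3: Cox model with censoring at removal.** All patients stay in their assigned arm. Bias arises only if removal is related to risk.

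**The case against.** A reader might infer that the two sections contradict each other and cannot both be followed. The text does not go that far. Section 3.2 speaks of leaving the study, not the analysis. Where the protocol means data exclusion it says so, as it does for screen failures in Section 3.1. A withdrawn patient can stay in the assigned arm of a Cox model, censored at withdrawal, and both sections are then respected.

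The one-arm wording has a benign reading too: restoring usual care only makes sense for Arm B, since Arm A already receives it. Withdrawal from Arm A is unaddressed, not barred. The family clause may mean only that whoever withdraws stops taking part. The trigger is withdrawal of consent, and nothing says that declining a coach contact counts as that. A general withdrawal clause may also stand in the consent form or in the detailed analysis plan that the heading of Section 5.2 mentions; neither was in the text checked here.

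These points stand, and they reduce the charge from contradiction to an undefined, one-sided rule. They do not remove it. Staff must act on the rule as worded, and no analysis plan can recover outcomes that were never collected.

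A reader might also infer that removal must flatter the coach because sicker patients leave. The documents give no support for that: if patients of lower risk are excluded, the bias runs the other way.

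**Conclusion.** The concern holds as a defect of definition that can bias the primary comparison. The rule is stated for one arm, is ambiguous about families, does not separate ending coaching from ending follow-up, and is not tied to the analysis set.

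Its size depends on what removal means in practice. Exclusion of 10% to 20% of Arm B gives anything from no bias, through risk ratios of 0.93 to 0.84 for high-risk leavers, to 1.05 to 1.10 for low-risk leavers. The path that needs no assumption about who leaves is the six-month count without an offset: counts that stop in Arm B alone favour the coach, with a rate ratio of about 0.93 to 0.87 for removal at month 2.

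All of this rests on assumed withdrawal rates, timings and risks, and on a baseline risk derived from the visit rate. If removal is rare, or outcomes continue to be collected, the effect is small or absent.

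**What to change.** - Write one withdrawal rule that applies to both arms.
- State that stopping coaching does not end the patient's follow-up, and that a family's withdrawal ends only the family's own participation.
- For a patient who withdraws consent for follow-up, keep all data to that date, continue record review where consent allows, and analyse in the assigned arm with Cox censoring at withdrawal.
- Add a follow-up-time offset to the six-month count model, as the 12-month count already has.
- Report withdrawals by arm, separating withdrawal from coaching and withdrawal from follow-up.

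Censoring and the offset deal only with loss that is unrelated to risk, so continued record review is the main protection against selective loss.

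The cost is protocol and consent wording, one model term, and the IRB modification that Section 6.4 requires for any change. No patients or procedures are added.

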3.3 Enrollment

The target number of subjects at the site is 128. Patient enrollment is anticipated to begin upon study approval and continue until 128 participants have enrolled.

4.0 MATERIALS AND METHODS

After a patient consents, the patient will be registered and entered into the project database and assigned an identification number. The subject's identification number will be used on all subject-specific documents and research-related forms.

During registration, patients will be randomized to two arms (Arm A: Usual Care Arm B: Health Care Coach Intervention). Specifically, the patients will be randomized into two arms by cancer type.

All patients will be surveyed over the course of the study regarding patient experience with care, patient satisfaction and overall health status and emotional and mental health status (using the CG-CAHPS: Clinician and Group Consumer Assessment of Healthcare Providers and Systems), advanced care planning, and symptom assessments (using the ESAS: Edmonton Symptom Assessment Scale) and healthcare use. A member of the project team, excluding the Health Care Coach, will administer the assessments and conduct an electronic health record review of all health care use at baseline, 3, 6, 9 and 12 months post-enrollment. Participants will provide consent for health record review at external facilities by signing a health release authorization form at each of the outcome assessment time periods. The symptom assessments will be administered at baseline for each patient in the intervention and control. Participant information should be entered into the local databases within 7 calendar days.

Arm A: Usual Care (Control) / No Intervention
 Patients in this arm receive "usual" care from their care team.

Arm B: Health Care Coach Arm / Intervention Group

The intervention will be comprised of a health care coach assignment with a baseline introduction (either telephonic or in-person) of the program followed by a visit (telephonic or in-person) with the health care coach within 1 week after the first oncology appointment or after a patient has recurrent disease to discuss goals of care. The health care coach is trained in engaging patients and families in goals discussion and in symptom management algorithms. The health care coach will use standardized educational information to inform contacts with the patient including PREPARE for your care and other educational content as determined by the study team. The health care coach will contact patient based on patients' ongoing needs (i.e. weekly to monthly) and will conduct symptom assessments based on patients' treatment plans and symptoms for 6-months post-enrollment. All symptoms that are scored 4 or above and/or change by 2 points from a prior assessment will be reviewed with the supervising nurse who will conduct standard usual care processes as determined by the facility. Health care coach will also conduct meetings with patient's family and caregivers at the same time intervals as needed and upon request. All health care coach interactions will be logged and will include date of the interaction, details of the interaction, and the duration of the interaction.

Choosing the Health Coach:

Possible health coaches are identified by [name], the site PI. Candidate health coaches are educated fully about the project and the workflow. Health coaches who are interested in engaging in this study are appointed. Health coaches do not need to have a clinical background to engage in this study.

Training the Health Coach:

The oncology care team of a triage RN, APN/PA, or PI will train the health care coaches and provide standardized training manuals. The manuals include a highly detailed workflow of the project, from enrollment to completion. Coaches will learn about what to say during patient contact, advanced care planning conversations, the administration of various psychosocial questionnaires, the study calendar, data management, and key contact information.

Supervising the Health Coach:

The health care coach will be supervised by the triage RN or APN/PA who provides oncology treatment support and also training. The triage RN or APN/PA will ensure that the protocol is carried out correctly and address any issues that may arise in the health care coach's workflow. The health care coach will participate in weekly meetings with the health coach in addition to daily supervision and will participate in monthly meetings with the rest of the project members (at both Stanford and St. Jude) to review study accrual and program goals. At these meetings, the health care coach will be responsible for providing a report on project progress and project issues.

Psychometric Measures

- 1. The Consumer Clinician and Group Consumer Assessment of Healthcare Providers and Systems (CG-CAHPS) will be used to assess patient satisfaction, overall health status, and overall emotional and mental health status. Information about the measure can be found here: https://cahps.ahrq.gov/Surveys-Guidance/CG/index.html
- 2. The Edmonton Symptom Assessment Scale (ESAS) will be used to measure the presence and degree of pain symptoms. The ESAS will be administered to the control group (at 0 months of diagnosis) and intervention group (every 2 weeks). The health care coach will embed the ESAS results for the control and intervention groups into Allscripts and alert the patient's provider that the results are available and if an issue exists.

[name] has used both of these measures with success before with a similar project completed at the Palo Alto Veterans Hospital (Palo Alto, CA). Information about this measure can be found here: http://www.npcrc.org/files/news/edmonton_symptom_assessment_scale.pdf

If patients feel discomfort while conducting their surveys they may choose to not complete them. If there are any psychological events that occur during the study, these will be reported to the NPOD and MOD via the site PI.

Site PI: [name]

[name] is responsible for site study supervision as well as the following: conducting biweekly meetings with all study members, troubleshooting recruitment and follow-up challenges, training the health care coaches, ensuring proper data collection, and general upkeep. The site PI is also responsible for interacting with the protocol director at Stanford, [name]. As this is [name] conception, and she piloted at another site, she will be able to provide [name] with specific advice and recommendations should challenges arise.

Protocol Director: [name]

[name] responsible for the overall study, submitting IRB and protocol amendments, corresponding with the site PI to help him troubleshoot any challenges in data collection or follow-up. [name] is also responsible for overseeing data analysis and manuscript publication.

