5.3 Sample Size

The goal is to reduce acute care use. Based on data from St. Jude Hospital, the mean number of acute care visits per member per year is 1.45. Local site oncologist in the pre-review assessment anticipated at least a 55% difference in risk of acute care use among participants in the intervention group as compared to the control group. For this trial, we estimated that a sample size of 128 participants would have at least 90% power with a 2-sided type I error rate of 0.05 to detect at least a

55% difference in risk of acute care use in the intervention group compared with the control group based on effect sizes from our ongoing VA pilot and other pilot studies. For this trial, we expect to obtain point estimates with an understanding that we may not reach significance in this study.

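### Health care use is reviewed at baseline, but prior acute care use is neither a listed balance variable nor a planned covariate; pre-specifying it is a cheap precision gain of uncertain size

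*Combined protocol and SAP*

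**What the plan says.** **Collection.** Section 4.0 has the team "conduct an electronic health record review of all health care use at baseline, 3, 6, 9 and 12 months post-enrollment". It gives no look-back period for the baseline review.

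**Balance check.** Section 5.2 compares the arms on "demographic (i.e., sex, age, race/ethnicity) and clinical variables (i.e., stage of cancer, diagnosis of cancer" (the bracket closes there). Prior health care use is not on the list.

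**Primary models.** For the composite and "individual ED and hospital use within 6 months post-enrollment, we will use Cox regression models". Six-month visit counts are compared "using General Estimating Equation with Poisson family, log link, and independent correlation". Neither sentence names a covariate.

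**Adjustment rule.** Later in 5.2, all analyses are to be adjusted for covariates found to differ between the arms. Age, race/ethnicity, stage and diagnosis are given as examples, introduced by *such as*.

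**Detailed plan.** The heading of 5.2 points to an attached detailed statistical analysis plan, which is not in the text supplied.

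**The concern.** A pre-randomization measure of the outcome is often among the better predictors of that outcome, and the plan already sends someone to the record at baseline. Nothing in the plan then uses what is found there. The balance list is introduced by *i.e.*, which reads as complete, so a difference in prior use might not be looked for. Adjustment depends on a difference being found.

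Two things are at stake. One is precision: the trial has 64 patients per arm and expects roughly 35 to 51 first events, depending on assumptions. The other is chance imbalance: if one arm happens to contain more frequent users, part of that difference can appear as a coach effect or hide one.

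**Working it through.** **1. The plan's own power figure**

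Inputs from 5.2 and 5.3: "The sample size of 128 participants (64 randomized to the intervention group and 64 randomized to the control group"; this "provides greater than 90% power to detect a 55% or greater difference in acute care use risk at 6-months follow-up"; "at least 90% power with a 2-sided type I error rate of 0.05"; and "the mean number of acute care visits per member per year is 1.45".

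- Control mean over 6 months: 1.45/2 = 0.725. The 6-month control risk is not stated. Assuming Poisson counts with no spread between patients, it is 1 − exp(−0.725) = 0.516.
- The 55% is read as relative: 0.45 × 0.516 = 0.232. An absolute fall of 55 points from 0.516 is impossible.
- Two proportions, 64 per arm: pooled SE 0.0855, unpooled SE 0.0818. Power = Φ[(0.284 − 1.96 × 0.0855)/0.0818] = 92.2%. The stated figure is reproduced.
- Cox model with the same risks: HR = ln(1 − 0.232)/ln(1 − 0.516) = 0.364; events = 64 × (0.516 + 0.232) = 47.9; power = Φ(|ln 0.364| × √(47.9/4) − 1.96) = 93.7%.
- If 55% means HR 0.45: intervention risk 1 − exp(−0.45 × 0.725) = 0.278; events = 64 × (0.516 + 0.278) = 50.8; power 81.2%.
- Poisson counts, rate ratio 0.45: SE = √(1/46.4 + 1/20.9) = 0.264; power 85.8%, or 57.2% if the variance is doubled.

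How much precision is needed therefore depends on what the 55% refers to and on overdispersion.

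**2. Rough gain from adjustment**

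Multiply the variance by (1 − r²), where r is the correlation of prior use with the outcome. The documents give no r, so the range is assumed. For the Cox model this is only a guide.

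| r | Equivalent sample-size gain, 1/(1 − r²) − 1 | Cox, HR 0.45 | Poisson, no overdispersion |
|---|---|---|---|
| 0 | 0% | 81.2% | 85.8% |
| 0.1 | 1% | 81.6% | 86.1% |
| 0.2 | 4% | 82.8% | 87.1% |
| 0.3 | 10% | 84.7% | 88.8% |
| 0.5 | 33% | 90.8% | 93.8% |

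The gain is under 2 points up to r = 0.2, and 3 to 3.5 points at r = 0.3.

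**3. Simulation**

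Settings: 64 per arm, control rate 1.45 per year, a gamma-distributed patient tendency with variance θ (assumed), and covariate log(1 + visits in the prior 6 months). *Shared* means prior and later use have the same tendency in every patient. *Half* means that this holds for half the patients.

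First, what θ does to the target. The control risk is 1 − (1 + 0.725θ)^(−1/θ), and the intervention risk uses 0.364 × 0.725 = 0.264 in place of 0.725.

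| θ | Control risk | Intervention risk at HR 0.364 | Risk reduction | Events | HR that restores 55% |
|---|---|---|---|---|---|
| 0.5 | 0.461 | 0.220 | 52% | 44 | 0.340 |
| 1 | 0.420 | 0.209 | 50% | 40 | 0.322 |
| 2 | 0.361 | 0.191 | 47% | 35 | 0.294 |

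So holding HR at 0.364 shrinks the effect as θ grows. Cox power, unadjusted to adjusted:

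| θ | HR 0.364, shared | HR 0.364, half | HR reset to 55%, shared | Gain, HR reset, half |
|---|---|---|---|---|
| 0.5 | 84 to 86% | 84.2 to 84.6% | 86 to 87% | 0 points |
| 1 | 75 to 81% | 73.6 to 74.1% | 84 to 87% | 1 point |
| 2 | 57 to 71% | 59.6 to 62.4% | 74 to 86% | 3 points |

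These use 2,000 trials per setting at HR 0.364 and 1,500 with HR reset. Repeat runs gave the same pattern, with gains within about 2 points of these. A separate simulation at rate ratio 0.45 with θ of 0.5 and 1 (800 trials per setting) gave gains of about 0.5 to 5 points for counts and 1 to 6 for Cox.

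**4. Type I error and chance imbalance**

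- Under no effect, rejection was 5.5% unadjusted and 5.8% adjusted. A second set of 3,000 trials per setting gave 4.6–5.1% and 4.9–5.3%.
- A standardized difference has SE of about √(2/64) = 0.177, so |difference| > 0.25 has probability of about 0.16. The simulation gave 15–16%.
- In those trials, with a shared tendency, the false-positive rate at θ = 0.5, 1 and 2 was 7.1, 7.9 and 11.7% unadjusted, against 6.1, 4.2 and 6.2% adjusted. Each rests on about 450–480 trials, with error of about 1 to 1.5 points.

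**The case against.** The strongest reply is that nothing here is invalid. Randomization protects the unadjusted test, section 5.3 expects point estimates that may not reach significance, and Appendix A titles the study a pilot. That stands, and it limits the point to an improvement.

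Four stronger readings are tempting, and the documents do not support them:

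- *The trial discards power it has already collected.* Section 4.0 gives no look-back window and does not say that earlier visits are abstracted as the outcome is. Records from outside facilities depend on a release signed at each outcome assessment. A usable prior count needs a specification that does not yet exist.
- *Prior use could not enter a model even if the arms differed.* The balance list reads as closed, but the adjustment list is open. Prior use is left out, not barred, and the detailed plan may name it.
- *Differences between patients are the main source of noise.* This is not shown. The small number of first events limits precision by itself.
- *Adjustment buys about 14 points of power.* That needs θ = 2, a fully shared tendency, and an HR of 0.364 that no longer corresponds to a 55% reduction. Section 3.2 enrolls newly diagnosed patients as well as recurrences. For the newly diagnosed, earlier use may be largely diagnostic and predict little.

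The point also overlaps with the broader weakness of choosing covariates by observed imbalance. A fixed covariate list would settle both, but only if prior use is put on it.

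**Conclusion.** The point holds as a recommendation. On the text supplied, prior acute care use is missing from the listed balance variables and is not a pre-specified covariate in either primary 6-month model; only the open-ended imbalance rule could bring it in. Adjusting for it regardless of balance would improve precision and guard against chance imbalance, with no visible cost in type I error.

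The gain cannot be sized from the documents. Under the assumed spreads it is about 0 to 3 points of Cox power if prior use is weakly informative. With a fully shared tendency and the 55% effect preserved, it is about 1 to 3 points at θ of 0.5 to 1 and about 12 at θ = 2. These figures assume a gamma tendency, a 6-month look-back and the same rate of use before and after enrollment. The planned unadjusted analysis remains valid.

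**What to change.** 1. In 4.0, define a fixed look-back for the baseline review, for example 6 months before randomization, using the same sources and visit definitions as follow-up, including outside facilities.
2. In 5.2, add prior ED visits and hospitalizations to the baseline table.
3. In 5.2, add a sentence such as: *The number of ED visits and hospitalizations in the 6 months before randomization enters the primary 6-month Cox and Poisson models as log(1 + count), regardless of observed balance.* Say whether the adjusted or the unadjusted estimate is primary, because an adjusted hazard ratio is conditional on prior use and is not the same quantity as the unadjusted one. Report both.
4. If the detailed analysis plan already does this, align 4.0 and 5.2 with it.

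The cost is one model parameter, a sentence or two, and a small addition to a record review already planned. No power gain should be claimed in advance.
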